3.7.3 Skin and Hypersensitivity Reactions

The number and percentage of subjects with any skin reactions (including skin hypersensitivity reactions) which are reported on the dedicated eCRF page and judged to be related to IP by the investigator will be summarized by treatment group and by SOC and PT.

3.7.4 New Onset Chronic Disease

New onset chronic diseases include, but are not limited to diabetes, autoimmune disease (eg, lupus, rheumatoid arthritis), and neurological disease (eg, epilepsy) and the type, incidence, and relationship to study investigational product will be summarized by treatment group and by SOC and PT based on MedDRA.

3.7.5 Subgroup Analyses

All AEs (including TEAEs, TESAEs, AESIs, NOCDs) and IP-related AEs (including TEAEs, TESAEs, AESIs, skin reactions, NOCDs) will be summarized by age group used as randomization stratum (age \leq 3.0 months, age > 3.0 to \leq 6.0 months, age > 6.0 months), weight on Day 1 (weight < 2.5 kg, weight \geq 2.5 kg and < 5 kg, weight \geq 5 kg on Day 1, Season 1 for Season 1 summary). Due to the small number of subjects with weight < 7 kg on Season 2 Day 1, Season 2 TEAEs will not be summarized by weight on Season 2 Day 1 (< 7 kg, \geq 7 kg), and will only be listed for subjects with weight < 7 kg on Season 2 Day 1. The Season 1 AEs will also be summarized for CLD subjects, CHD subjects, subjects with GA < 29 weeks, subjects with GA < 29 weeks and without CLD or CHD, and CLD subjects with GA < 32 weeks. The Season 2 AEs will also be provided for CLD subjects, CHD subjects, and CLD subjects with GA < 32 weeks.

TEAEs, TESAEs, AESIs, IP-related skin reactions (including skin hypersensitivity reactions) will also be summarized by timing relative to dosing ('within 1 day', 'within 3 days', 'within 7 days', 'within 14 days'). As subjects in the MEDI8897 group will receive both MEDI8897 and placebo dosing, corresponding AEs for these subjects will be broken down further by the dosing category (MEDI8897 or placebo). For example, to summarize AEs within 7 days, if a subject receives the first dose which contains MEDI8897, and 4 subsequent doses which only contains placebo, then the AEs within 7 days of the first dose will be included in the MEDI8897 category, AEs within 7 days of any of the four doses will be included in the placebo category; if a subject receives 5 doses of palivizumab, then all the AEs within 7 days of any of the 5 doses will be included in the palivizumab category. If an AE occurred within 14 days relative to both the replacement dose and next dose, we will consider the AE associated with the replacement dose only and count it within the appropriate timing relative to the replacement dose.

TEAEs, TESAEs, AESIs, and IP-related skin reactions (including skin hypersensitivity reactions) will also be summarized by number of active doses received within each treatment group. The corresponding categories are: no more than planned active doses, more active doses than planned, further broken down by: 1 more active dose than planned, 2 more active doses than planned etc.

In addition, TEAEs occurring within 1 day, 3 days, 7 days, and 14 days post dose by age at randomization (≤ 3.0 months, > 3.0 to ≤ 6.0 months, > 6.0 months) will also be summarized,

respectively. Similar summaries will be provided by timing relating to the first dose for each season.

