2.2 Study Design

This is a randomized, double-blind, palivizumab-controlled study in which approximately 900 palivizumab-eligible infants entering their first RSV season will be enrolled into one of 2 cohorts (Figure 1): (1) preterm cohort, including approximately 600 preterm infants (\leq 35 weeks gestational age [GA]) without CLD/CHD, or (2) CLD/CHD cohort, including approximately 300 infants with CLD of prematurity or hemodynamically significant CHD. A minimum of 100 infants with hemodynamically significant CHD will be enrolled. Within each cohort, randomization will be stratified by hemisphere (northern, southern) and subject age at the time of Season 1 randomization (\leq 3.0 months, > 3.0 to \leq 6.0 months, > 6.0 months).

Season 1, Preterm and CLD/CHD Cohorts

All subjects will be randomized 2:1 to either the MEDI8897 group (approximately 600 subjects, including approximately 400 subjects in the preterm cohort and approximately 200 subjects in the CLD/CHD cohort) or palivizumab group (approximately 300 subjects, including approximately 200 subjects in the preterm cohort and 100 subjects in the CLD/CHD cohort). Subjects in the MEDI8897 group will receive a single fixed IM dose of MEDI8897 followed by 4 once-monthly IM doses of placebo. The MEDI8897 dose level will be stratified by weight band, ie, 50 mg for infants weighing < 5 kg or 100 mg for infants weighing \ge 5 kg. Subjects in the palivizumab group will receive 5 once-monthly IM doses of 15 mg/kg palivizumab.

Season 2, CLD/CHD Cohort Only

[figure not shown]
- Subjects with CLD/CHD ≤ 24 months of age who were randomized to the MEDI8897 group for Season 1 will receive a single fixed IM dose of 200 mg MEDI8897 followed by 4 once-monthly IM doses of placebo (approximately 200 subjects).
- Subjects with CLD/CHD ≤ 24 months of age who were randomized to the palivizumab group for Season 1 will be re randomized 1:1 to either the MEDI8897 group or the palivizumab group. Subjects in the MEDI8897 group will receive a single fixed IM dose of 200 mg MEDI8897 followed by 4 once monthly IM doses of placebo (approximately 50 subjects). Subjects in the palivizumab group will receive 5 once monthly IM doses of 15 mg/kg palivizumab (approximately 50 subjects).

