3.7.1 Adverse Events and Serious Adverse Events

Adverse events and serious adverse events will be coded by MedDRA version 22 or higher and the type, incidence, severity and relationship to study investigational product will be summarized by treatment group. Specific AEs will be counted once for each subject for calculating percentages. In addition, the total number of AEs will also be provided. In addition, if the same AE occurs multiple times within a particular subject, the highest severity and level of relationship observed will be reported. All treatment-emergent AEs (TEAEs) and treatment-emergent SAEs (TESAEs) occurring through Day 361 will be summarized overall, as well as categorized by MedDRA SOC and PT. In addition, the TEAEs occurring at 1% or higher in either treatment group will be reported by PT.

Nontreatment-emergent AEs/serious adverse events (SAEs), defined as AEs/SAEs that occur prior to the administration of investigational product, or after Day 361, Season 1 for preterm cohort, or after Day 361, Season 1 and prior to Day 1, Season 2 for CHD/CLD cohort, or after Day 361, Season 2 for CHD/CLD cohort, or pre-planned surgeries that are coded with PT "Cardiac Operation" and occur during the study for CHD subjects will be presented in the listings.

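### The any-dose timing tables in SAP 3.7.5 set one post-injection window for MEDI8897 beside five for palivizumab, with no per-injection denominator and no statement of which timing table compares the drugs

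*SAP*

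**What the plan says.** SAP 3.7.5 (Subgroup Analyses) plans summaries of treatment-emergent AEs (TEAEs), treatment-emergent serious AEs (TESAEs), AEs of special interest (AESIs) and product-related skin reactions by time since dosing, with windows of 1, 3, 7 and 14 days. Infants in the MEDI8897 group receive one active and four saline injections, so "corresponding AEs for these subjects will be broken down further by the dosing category (MEDI8897 or placebo". The 7-day worked example sets the rule:

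- After one MEDI8897 dose and four placebo doses, "then the AEs within 7 days of the first dose will be included in the MEDI8897 category".
- For the placebo doses, "AEs within 7 days of any of the four doses will be included in the placebo category".
- For an infant given five palivizumab doses, "all the AEs within 7 days of any of the 5 doses will be included in the palivizumab category".

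SAP 3.7.1 gives the counting rule: "Specific AEs will be counted once for each subject for calculating percentages". It also provides total numbers of AEs. SAP 3.7.5 names no per-injection denominator.

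The last paragraph of SAP 3.7.5 plans TEAEs in the same four windows by age at randomization, then adds: "Similar summaries will be provided by timing relating to the first dose for each season".

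**The concern.** An infant can enter the MEDI8897 category through one window per season, the placebo category through four, and the palivizumab category through five (before any replacement dose after bypass surgery). If each infant counts once, the expected percentage rises with the number of windows even when every injection carries the same risk. Read side by side, the columns favour MEDI8897 over palivizumab under no difference, and also make saline look worse than MEDI8897.

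The primary objective is safety and tolerability of MEDI8897 compared with palivizumab, and events soon after injection bear directly on tolerability. The analysis is descriptive, so readers will judge by setting percentages next to each other. The SAP does not say which timing table is meant for that comparison.

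**Working it through.** **The plan's own figure.** The documents give no figure for the timing tables. The only stated safety figure is a 95% chance of at least one AE among 600 infants at a true rate of 0.5% (SAP 2.4). It reproduces: 1 − 0.995^600 = 0.951.

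**Inputs**
- Season 1: about 600 infants on MEDI8897 and 300 on palivizumab (SAP 2.2).
- Windows per infant, k: MEDI8897 1, placebo 4, palivizumab 5 (SAP 3.7.5).
- Planned windows: 600 × 1 = 600; 600 × 4 = 2,400; 300 × 5 = 1,500.
- Illustrative one-window TEAE risk, p, from the Phase 2b study (Protocol 1.4.1): 2.5% within 1 day (both groups) and 12.5% within 7 days (MEDI8897; placebo was 15.2%).
- Assumed: the same p at every injection in both arms.

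**Independent windows.** P(at least one event) = 1 − (1 − p)^k.

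| Window | p | MEDI8897, k = 1 | Placebo, k = 4 | Palivizumab, k = 5 | Palivizumab ÷ MEDI8897 |
|---|---|---|---|---|---|
| 1 day | 2.5% | 2.5% | 9.6% | 11.9% | 4.8 |
| 7 days | 12.5% | 12.5% | 41.4% | 48.7% | 3.9 |

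**Correlated windows.** Some infants are more prone to events than others. With a beta-binomial model and within-infant correlation ρ, set M = 1/ρ − 1, a = pM and b = (1 − p)M. Then P(at least one in 5) = 1 − ∏ (b + i)/(a + b + i), for i = 0 to 4.

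| ρ | Palivizumab, 1 day (ratio to 2.5%) | Palivizumab, 7 days (ratio to 12.5%) |
|---|---|---|
| 0.1 | 10.0% (4.0) | 42.3% (3.4) |
| 0.3 | 7.4% (3.0) | 32.8% (2.6) |
| 0.5 | 5.6% (2.2) | 25.8% (2.1) |
| 1 | 2.5% (1.0) | 12.5% (1.0) |

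The imbalance disappears only at ρ = 1.

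**Chance of a misleading ordering, 600 vs 300 infants.**
- Equal risk: MEDI8897 shows the lower percentage in 98% to 100% of trials for ρ from 0 to 0.5, at either p.
- MEDI8897 truly doubling the 1-day risk (5.0% per injection against 2.5%): it still shows the lower percentage in more than 99% of trials at ρ = 0 or 0.1, 91% at 0.3 and 62% at 0.5.
- Rare events, equal risk, independent windows: at an assumed 0.1% per window MEDI8897 is lower in about 74% of trials; at 0.05%, about 51%, with 36% ties.

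**Comparisons that are balanced.**
- First dose against first dose: 2.5% vs 2.5%, and 12.5% vs 12.5%.
- MEDI8897 group over all five injections against palivizumab, if saline injections carry the same p: 11.9% vs 11.9%, and 48.7% vs 48.7% (independent windows).
- Per injection, at p = 2.5%: 600 × 0.025 = 15 expected windows with an event, 15/600 = 2.5%; and 1,500 × 0.025 = 37.5, 37.5/1,500 = 2.5%. These expected rates are equal whatever the correlation.

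**The case against.** Much of the remedy is in the plan or close to it.

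- **First-dose summaries are planned.** They set one window against one. For TEAEs this is clear. For TESAEs, AESIs and skin reactions it is not, because the sentence follows one limited to TEAEs by age.
- **A group total is implied.** A further breakdown of the MEDI8897 group presupposes a total over all five injections, which would be five windows against five. This is a fair reading, but the worked example defines only the three categories.
- **The main safety tables are not affected.** TEAEs and TESAEs through Day 361, AESIs and new onset chronic diseases are each summarised by treatment group (SAP 3.7.1, 3.7.2, 3.7.4). No hypothesis test is planned and no decision rule uses the timing tables. A reader might infer that the primary safety comparison is biased; the documents do not support that.
- **The illustrative risks are all-cause TEAEs in healthy preterm infants.** The 7-day rate was higher on placebo than on MEDI8897, so much of it is probably background illness. AESIs were far rarer: 0.5% on MEDI8897 in the Phase 2b safety summary. A reader might infer that the number of windows fixes the ranking. It does not, as the 62% figure and the rare-event results show.
- **Regimen burden is a fair question.** One active injection against five is a real difference between the treatments. It is a different question from drug tolerability per injection, and this split does not answer it cleanly, because events after the four saline injections are moved to another column.
- **Table layouts sit elsewhere.** SAP section 1 refers to a separate programming plan that is not available here, so the final columns and denominators may already address some of this.

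These points narrow the finding to the any-dose tables and the SAP's silence on which version compares the drugs. They do not make the one-versus-five contrast interpretable as written.

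**Conclusion.** The concern holds for one set of tables. In the any-dose timing summaries, the per-infant percentages in the MEDI8897 and palivizumab categories are not comparable. At equal per-injection risk palivizumab shows about 4 to 5 times the MEDI8897 percentage with independent windows, and about twice at a within-infant correlation of 0.5. The direction follows from the counting rule. The size rests on the Phase 2b TEAE risks, equal risk at every injection, the assumed correlations and full dosing without replacement doses. For AESIs and other rare events the ordering in a single trial is much less certain.

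It would be wrong to conclude that the plan has no like-for-like post-injection comparison. One is planned for TEAEs and another is implied. What is missing is explicit coverage of the other three event classes, an explicit five-injection total, a per-injection denominator, and a statement of which table compares the drugs.

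**What to change.** In SAP 3.7.5 and the matching table templates:

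1. State that the first-dose timing summaries cover TEAEs, TESAEs, AESIs and product-related skin reactions, and that they are the between-drug comparison of events after injection.
2. In the any-dose table, show explicitly the MEDI8897 group over all five injections (active and saline) beside palivizumab.
3. For the MEDI8897, placebo and palivizumab categories, give the number of injections, counting replacement doses in the category of the drug given, and a per-injection rate: windows with at least one event divided by injections given. If a per-infant one-versus-five contrast is kept, label it as a regimen comparison.

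The cost is SAP wording and a column or denominator in tables already planned. No new data and no change in trial conduct are needed. The trade-off is slightly more table work, and MEDI8897 will look less favourable relative to palivizumab than in the one-versus-five contrast.

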3.1.2.3 Season 1 or Season 2, CLD/CHD Cohort - Replacement Dose

Subjects in the CLD/CHD cohort who undergo cardiac surgery with cardiopulmonary bypass after receipt of Dose 1 but prior to receipt of Dose 5 will receive a replacement dose of the study drug that they received for Dose 1 immediately following the surgery when determined by the physician to be medically stable for an IM injection. Any subsequent doses of study drug will continue to be given according to the protocol-specified dosing schedule. In subjects requiring multiple surgeries during the same season, the dosing and timing scheme described below should be followed relative to the most recent replacement dose.

Details for the replacement dose by randomized group are presented below.

MEDI8897 Group

- Season 1
 - Subjects undergoing surgery < 90 days post first dose who originally received 50 mg MEDI8897 will receive a single 50-mg MEDI8897 IM replacement dose if < 5 kg body weight at time of replacement dosing or a single 100-mg MEDI8897 IM replacement dose if \geq 5 kg body weight at time of replacement dosing.
 - Subjects undergoing surgery < 90 days post first dose who originally received 100 mg MEDI8897 will receive a single 100-mg MEDI8897 IM replacement dose.
 - Subjects undergoing surgery \geq 90 days post first dose who originally received either 50 mg or 100 mg MEDI8897 will receive a single 50-mg MEDI8897 IM replacement dose.
- Season 2
 - Subjects undergoing surgery < 90 days post first dose will receive a single 200-mg MEDI8897 IM replacement dose.
 - Subjects undergoing surgery \geq 90 days post first dose will receive a single 100-mg MEDI8897 IM replacement dose.

Palivizumab Group

Subjects will receive a 15 mg/kg palivizumab IM replacement dose. Thereafter, doses should be given according to the protocol-specified dosing schedule.

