3.2.3 Rationale for Endpoints

MEDI8897 is being developed to provide RSV immunoprophylaxis for all infants entering their first RSV season and children with CLD of prematurity or hemodynamically significant CHD entering their first and second seasons. The primary endpoint for this study is safety and tolerability, with the aim of comparing the profiles for MEDI8897 and palivizumab in this population. The standard measures of TEAEs/TEAEs, AESIs, and NOCDs will be used for this assessment. All subjects will be followed for approximately 1 year after the last dose of MEDI8897. Subjects with CLD/CHD who receive MEDI8897 for Season 1 and Season 2 and subjects who receive a replacement dose of MEDI8897 after cardiopulmonary bypass will provide data for the safety assessment of infants who receive more than a single dose of MEDI8897.

Serum concentration of MEDI8897 at selected time points will be evaluated as a secondary endpoint to confirm that serum concentrations are maintained at an efficacious level for at least 5 months after dosing. Palivizumab serum concentrations will also be evaluated. MEDI8897 and palivizumab PK data will be summarized by non-compartmental analysis. Additionally, serum concentration data will be used to characterize the PK of MEDI8897 in infants using a population PK approach separately. For infants who require hospitalization for

LRTI or any respiratory infection, an additional serum sample for measurement of MEDI8897/palivizumab concentration and ADA will be obtained contemporaneous with time of hospitalization. Exposure-response analysis will be performed to relate MEDI8897 serum concentrations and efficacy endpoints (LRTI including RSV-associated hospitalization).

To determine MEDI8897 and palivizumab serum levels post dosing and to correlate with the potential development of ADA, serum concentrations will be measured up to 360 days post Dose 1 (when MEDI8897 would be given) for both Season 1 and, as applicable, Season 2. ADA to MEDI8897 and to palivizumab will be measured at selected time points throughout the study and up to 360 days post Dose 1 for each season as well.

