3.7 Safety Analyses

All safety analyses will be conducted on as-treated population.

For each season as well as the two consecutive seasons combined (ie, Season 1, Season 2, Season 1 + Season 2) the summaries will be provided using the respective as-treated population. The Season 1 summaries will also be provided for each cohort (pre-term, CHD/CLD).

For each season, all safety analyses planned will be presented. For Season 1 + Season 2, number and percentage of subjects with treatment-emergent adverse events (TEAEs), treatment-emergent serious adverse events (TESAEs), adverse events of special interest (AESIs), IP-related skin reactions, and new onset chronic diseases (NOCDs) will be summarized by MedDRA System Organ Class (SOC) and Preterm Term (PT) for palivizumab/palivizumab and MEDI88987/MEDI8897 groups. The Season 1 + Season 2 summaries will be presented for CLD/CHD cohort, for CLD subjects and CHD subjects, separately.

For Season 2 summaries and Season 1 + Season 2 summaries, direct comparison between MEDI8897/MEDI8897 with palivizumab/palivizumab groups are subject to potential bias if the dropouts of Season 1 are associated with safety.

 Table 3
 Reporting Period of Treatment-emergent Adverse Events

Reporting Period	Definition of Treatment-emergent AEs	
Season 1	Any AEs that started on/after date of 1 st dose of Season 1, and prior to the end of Season 1, Day 361 or the last day prior to 1 st dose of Season 2, whichever comes earlier.	
Season 2	Any AEs that started on/after date of 1st dose of Season 2 and prior to the end of Season 2, Day 361.	
Season 1 + Season 2	Any AEs that started on/after date of 1st dose of Season 1 and prior to the end of Season 2, Day 361.	

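### The safety table by number of active doses counts events that began before the extra dose, and its above-plan row fills differently in the two arms

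*SAP*

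**What the plan says.** SAP 3.7.5 states that TEAEs, TESAEs, AESIs and product-related skin reactions "will also be summarized by number of active doses received within each treatment group". The two main rows are "no more than planned active doses, more active doses than planned", and the second is broken down further by the number of extra doses. The section gives no number for the plan and no onset window for this table.

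Without its own window, the table inherits SAP Table 3 (section 3.7). For Season 1 that table starts at the first dose of the season, "and prior to the end of Season 1, Day 361 or the last day prior to" the first Season 2 dose. Events before an extra dose are inside it.

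The extra dose comes from Protocol 3.1.2.3: CLD/CHD infants who have cardiac surgery with bypass "after receipt of Dose 1 but prior to receipt of Dose 5 will receive a replacement dose", once the physician judges them stable enough for an injection. The scheduled regimens differ. SAP 2.2 states that MEDI8897 infants "will receive a single fixed IM dose of MEDI8897 followed by 4 once-monthly IM doses of placebo", whereas palivizumab infants have five monthly active doses.

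Protocol 3.2.3 says that infants dosed with MEDI8897 in both seasons, and those given a replacement dose, "will provide data for the safety assessment of infants who receive more than a single dose of MEDI8897".

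**The concern.** The row label says dose count, but membership is decided after Dose 1, mainly by whether the infant had bypass surgery. All events of the season then follow the infant into that row. An infant who deteriorates unexpectedly, is operated on, has a complication, recovers and only then receives the replacement dose contributes those earlier events to the extra-dose row. The dose cannot have caused them.

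The same label also selects differently by arm, because the threshold is low on MEDI8897 and high on palivizumab. The two above-plan rows then hold different selections of surgical infants, and a reader who compares them is not comparing like with like.

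Safety is the primary objective, and replacement-dose infants are one of two named sources on repeat MEDI8897 dosing. A table that mislabels their events could suggest a harm of repeat dosing that is really the surgical course, or blur a real signal. SAP 3.5.1.2 and 3.7 warn of dropout bias in the Season 2 comparisons; no such warning is attached here.

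**Working it through.** **The plan's own figure.** The dose-count table has none. The only safety figure is the 95% chance of at least one event among 600 infants at a true rate of 0.5%: 1 − 0.995^600 = 0.951. It reproduces, but it concerns the whole MEDI8897 arm.

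**Which events enter the row.** For an infant with bypass in Season 1:
- Dose 1 to replacement dose: counted (Table 3), although the extra dose has not been given.
- Replacement dose to end of season: counted, and rightly placed.
- A pre-planned operation carrying the cardiac-operation preferred term: listed only (SAP 3.7.1).
- Admissions or operations planned for pre-existing disease that did not worsen unexpectedly: normally not AEs (Protocol 5.1 and Appendix A).
- Complications of a planned procedure: AEs or SAEs (Protocol 5.1).

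So the misplaced events are unexpected deterioration and complications before the replacement dose. Because that dose waits for stability, such complications tend to precede it.

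**How the row fills by arm.** Take planned as 1 and 5 per season (implied by the regimens, not stated), one replacement dose, and no deaths.
- MEDI8897: Dose 1 was given, so 1 + 1 = 2 > 1. The infant always enters.
- Palivizumab: Dose 1 plus the replacement leaves four scheduled doses, all needed to reach 6 > 5. With independent miss probability m, the chance of entering is (1 − m)^4.
- m = 0: 100%. m = 2%: 0.98^4 = 92%. m = 5%: 0.95^4 = 81%. m = 10%: 0.90^4 = 66%.

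The miss rates are assumptions. The SAP itself expects missed active doses (sections 3.4.3, 3.5.1.3 and 3.10). Death before Dose 5 acts the same way: in the simulation below, where bypass infants are taken to receive the replacement, all who die within 30 days of surgery are in the row on MEDI8897, against about 6% to 18% on palivizumab.

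**Direction and size with no drug effect.** With season TESAE risk b without surgery and added surgical risk s, the row's expected risk is 1 − (1 − b)(1 − s). Take b = 15%, inside the Phase 2b range of 10.4% to 16.7% (Protocol 1.4.1, healthy preterm infants). Then s = 0, 20%, 30%, 50% gives 15%, 32%, 40.5%, 57.5%. The output only restates s, which the documents do not give.

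A fuller simulation assumed CHD in 1/9 of infants (the minimum 100 of 900), bypass in 10% to 30% of them on Days 14 to 121, background SAE risk 10.4%, and 3% post-surgical deaths. MEDI8897 infants with an SAE, above plan against the rest:
- CHD hazard ×1, no complications: 12–13% against 10%. The gap comes from the assumed deaths.
- CHD hazard ×2, 20% complications: 38% against 11%.
- CHD hazard ×4, 50% complications: 69% against 12–13%.

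A counter-case has no complications, equal hazard, no post-surgical deaths, and 10% of CHD infants dying early. The above-plan row is then better within CHD (15% against 21%) and about level in the whole CLD/CHD cohort (15% against 13%).

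SAEs beginning before surgery occurred in about 2% to 8% of bypass infants. The simulation does not split complications into before and after the replacement dose.

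**Group sizes.** About 67 MEDI8897 and 33 palivizumab CHD infants at 10% to 30% bypass give about 7–20 and 3–10. At m = 5%, (1 − 0.8145) × 3.3 to 10 = 0.6 to 1.9 palivizumab infants change row. With no events in 7 or 20 infants, the one-sided 95% upper bound, 1 − 0.05^(1/n), is 35% or 14%.

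**The case against.** A reader might infer that the above-plan row must look worse whatever the drug does. The documents do not support that. Infants who die or withdraw before surgery stay in the other row, which can reverse the direction within CHD, and nothing in the documents shows that surgery raises AESIs or skin reactions judged product-related.

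A reader might also suppose that every surgical admission is charged to extra dosing. Planned admissions and operations for pre-existing disease are normally not AEs, and exclusion criterion 6 keeps out infants with surgery anticipated within two weeks of randomization.

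Nor does the protocol rest repeat-dose safety on this table alone. Section 3.2.3 also names infants dosed in both seasons, and SAP 3.7 summarizes those separately.

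The plan has partial safeguards. SAP 3.7.5 has a table by time since dosing, which assigns an event falling within 14 days of both doses to the replacement dose, and summaries for CHD infants. Mixed-dose infants are listed (3.4.3), and further tables may follow review of the listings (3.7.7). The analysis is descriptive. A palivizumab infant with five active doses has, literally, not exceeded plan.

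All of this stands, and it limits the point. It does not correct this table: the timing table covers short windows only, the CHD summaries do not separate events before and after the extra dose, and a literally correct count still gives rows that mean different things in the two arms.

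**Conclusion.** The point holds in limited form. That pre-dose events enter the extra-dose row follows directly from SAP 3.7.5 read with Table 3 and needs no assumption about rates. The unequal filling follows if planned means 1 and 5 active doses; it is material as a proportion but small in infants, about one or two on palivizumab at a 5% miss rate.

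The expected direction for TEAEs and TESAEs is unfavourable to the above-plan row, but this is not certain. Bypass, complication and miss rates and the CHD hazard are all assumed, so the figures above illustrate the mechanism and do not estimate the bias. No claim is made for AESIs or skin reactions. A modest change is worth making because the data exist and the misattribution is avoidable.

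**What to change.** In this table of SAP 3.7.5:
- Group by receipt of a replacement dose, yes or no, by the same rule in both arms, with the number of replacement doses as a further breakdown.
- For yes, count only events with onset on or after the first replacement dose. Tabulate earlier events under the planned regimen.
- Show the replacement-dose infants of the two arms side by side.
- List extra active doses due to dosing error separately.
- Footnote that the yes/no contrast within an arm remains confounded by surgery, and that observation after a replacement dose is shorter than the season.

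The cost is SAP wording and an onset-date filter on data already collected. The groups stay small, the row will hold fewer events, and peri-operative events after the replacement dose remain in it. The change removes a misattribution; it does not isolate a drug effect.
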